CTC-AE	Common Terminology Criteria for Adverse Events, version 4.0
CTFG	Clinical Trial Facilitation Group
DBP	Diastolic Blood Pressure
DSMB	Data and Safety Monitoring Board
ECG	electrocardiogram
EDTA	ethylenediaminetetraacetic acid
Frei	relative bioavailability
GCP	good clinical practice
GGT	gamma-glutamyi transferase
GM	geometric mean
Н	hours
HIV	Human Immunodeficiency Virus
HR	heart rate
1B	Investigator's Brochure
IBD	Inflammatory Bowel Disease
ICF	informed consent form
ICH	International Conference on Harmonization
IEC	Independent Ethics Committee
IL-22	Interleukine 22
IMP	Investigational Medicinal Product
Max	maximum
MedDRA	Medical Dictionary for Regulatory Activities
	miligram
mg	iningen minimum
Min	microni
miR	militer
mL	millimeters of mercury
mmHg	milimeters of mercuity No Observed Adverse Effect Level
NOAEL	
o.d.	Once Daily
PCSA	potentially clinically significant abnormalities
PD	pharmacodynamics
PK	pharmacokinetics
PT	preferred term heart-rate—corrected QT interval (time between the start of the Q wave and the end of the T wave in the heart's electrical cycle) using Bazett's
QTc	formula
R	Accumulation ratio
SAE	serious adverse event
SBP	systolic blood pressure
SD	standard deviation
SEM	standard error of the mean
SF-36	Quality of Life Questionnaire
SOC	system organ class
t _{1/2}	terminal half-life
TEAE	treatment emergent adverse event
tiag	interval between administration time and the sampling time preceding the first concentration above the limit of quantification
t _{mex}	time to peak plasma concentration
UC	Ulcerative Colitis
Vd/F	volume of distribution
varr vs.	Versus
12.	*5.700

1. INTRODUCTION AND STUDY RATIONALE

Ulcerative Colitis (UC) 1.1.

1.1.1. Disease

[figure not shown]

ABX464 rationale 1.2.

1.2.1. Investigational treatment description

[figure not shown]

[figure not shown]
1.2.2. Investigational product description

1.2.3. Investigational product Mode of Action

[figure not shown]
1.2.4. Rationale for the development of ABX464 in Ulcerative Colitis

[figure not shown]

1.2.5. Preclinical data of ABX464

1.2.5.1. Non-clinical background information

1.2.6. Previous clinical experience with ABX464

2. STUDY OBJECTIVES AND ENDPOINTS

2.1. Primary Objective

The primary objective of the study is to evaluate the safety of ABX464 given at 50 mg once daily versus Placebo in subjects with Moderate to Severe Active Ulcerative Colitis who have failed or are intolerant to immunomodulators, Anti-TNFα, vedolizumab and/or corticosteroids.

2.2. Secondary Objectives

The secondary objectives are:

- To evaluate the effect of ABX464 on the expression of IL-22 in serum and rectal/sigmoidal tissue compared to placebo in Subjects with Moderate to Severe Active Ulcerative Colitis.
- To evaluate the effect of ABX464 on miR-124 expression in whole blood (PAXgene®) and in tissue (RNA later) vs placebo in Subjects with Moderate to Severe Active Ulcerative Colitis.
- To evaluate the effect of ABX464 on the rectal/sigmoidal infiltrates (Geboes score) vs placebo in Subjects with Moderate to Severe Active Ulcerative Colitis.
- To evaluate the effect of ABX464 on the rectal microbiome compared to placebo in subjects with Moderate to Severe Active Ulcerative Colitis
- To evaluate the effect of ABX464 on endoscopic remission vs placebo in Subjects with Moderate to Severe Active Ulcerative Colitis.
- To evaluate the effect of ABX464 on clinical remission and response vs placebo in subjects with Moderate to Severe Active Ulcerative Colitis.
- To evaluate the effect of ABX464 on Quality of Life (QoL) measured by the SF-36 questionnaire vs placebo in Subjects with Moderate to Severe Active Ulcerative Colitis.
- To assess the Pharmacokinetics parameters of ABX464 in Subjects with Moderate to Severe Active Ulcerative Colitis.

2.3. Primary Endpoint

The primary endpoint of this study is defined as the number of incidences of treatment-emergent adverse events in the ABX464 treated subjects compared to placebo.

2.4. Secondary Endpoints

The secondary endpoints of this study are:

Primary efficacy endpoint:

The proportion of subjects receiving ABX464 with clinical remission according to the Total Mayo Score
at week 8 compared to placebo. Remission exclude friability and is based on total Mayo score ≤ 2 with
no individual sub-score > 1.

Other secondary endpoints:

- The change from screening in IL-22 expression levels in serum and rectal/sigmoidal tissue at week 8 compared to placebo.
- The change from baseline in microRNA-124 levels in whole blood (PAXgene®) and in tissue (RNA later) at week 4 and week 8 compared to placebo.
- The change from baseline in fecal calprotectin levels at week 4 and week 8 compared to placebo.
- The change from screening in the histopathology/infiltrate (rectal/sigmoidal biopsies) assessed by the

Geboes score at week 8 compared to placebo.

- The change from screening in rectal microbiota using taxonomic markers at week 8 compared to placebo.
- The change from screening in Total Mayo Score in subjects receiving ABX464 at week 8 compared to placebo.
- The change from baseline in Partial Mayo Score in subjects receiving ABX464 at week 4 and week 8 compared to placebo.
- The proportion of subjects achieving endoscopic remission at week 8. Endoscopic remission is defined as a Mayo endoscopic sub-score of 0.
- The proportion of subjects achieving improvement in endoscopic appearance at week 8. Improvement of endoscopic appearance is defined as a Mayo endoscopic sub-score of ≤ 1.
- The proportion of subjects achieving a symptomatic remission at week 8. Symptomatic remission is
 defined as a total Mayo Score ≤ 2 with no individual sub-score > 1 and rectal bleeding and stool
 frequency sub-scores of 0.
- The time to UC worsening after week 8.
- The serum concentration evaluation of ABX464 and its metabolites levels.
- The scores and changes from baseline in SF-36 Questionnaire scores at week 4 and week 8.
- The number of incidences of treatment-emergent serious adverse events.
- The number of incidences of treatment-emergent adverse events of special interest.
- The number of incidences of adverse events leading to investigational product discontinuation.
- The number of incidences of specific laboratory abnormalities.

[figure not shown]
3. INVESTIGATIONAL PLAN

3.1. Study design

3.1.1. Design and methodology

This Phase IIa study is an 8-week, double-blind, placebo-controlled, randomized study aimed at evaluating the safety and the efficacy of ABX464 given once a day (o.d) at 50 mg in subjects with moderate to severe Active Ulcerative Colitis who have failed or are intolerant to immunomodulators, Anti-TNF α , vedolizumab and/or corticosteroids followed by a one-month follow-up period.

Eligible subjects will be randomized according to a 2/1 ratio in two different groups of treatments according to the following study design.

Upon screening visit (D-14), eligible subjects will be checked for eligibility.

Subject eligibility will be confirmed by the medical staff based of the endoscopy central reading and on the laboratory results performed at screening visit. If eligibility is confirmed, then the subject will be randomized using the eCRF.

At Day 0, study drug (ABX464 or its matching placebo) will be added on top of this background therapy for the next 56 days. ABX464 or its matching placebo will be given once a day at 50 mg.

For subjects receiving oral corticosteroids during the study treatment period, tapering of steroids should start at week 4 at a rate of prednisone or prednisone equivalent 5 mg/week for 4 weeks to discontinuation. However, this study procedure is left to the Investigator's discretion.

The dose of 50 mg of the study drug has been selected based on the reassuring safety data accumulated on the 50 mg o.d. from previous studies and the high exposure in ABX464-NGluc (active metabolite) at this dose.

Eligible subjects will be randomized according to a 2/1 ratio in two different groups of treatments.

Randomization will be stratified according to the following factors: concomitant treatment with corticosteroids and previous TNF antagonist exposure.

Randomized subjects will be seen at the investigational site every week during the first month of treatment and then every two weeks during the second month. Flexible sigmoidoscopy with rectal and/or sigmoidal biopsies will be performed again at week 8.

The DSMB will meet after every 3 subjects are recruited in order to review on a regular basis the safety profile of this dose level and to recommend, if appropriate, the continuation of the study.

The sample size in this Proof of Concept study is 20 subjects receiving ABX464 and 10 subjects receiving Placebo (i.e. a total of 30 subjects).

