3.2. Duration of study participation

Eligible subjects will be enrolled in the present study at the screening visit 2 weeks prior to the first dosing. Subjects will be treated for 8 weeks. All subjects willing to carry on the study treatment will be able to take part in an open-label study (ABX464-102).

In any other cases, the subjects will exit the study (EoS visit to be performed within a week after last dosing) and will be treated according to the standard of care.

Thus, the total duration of the study participation is 11 weeks.

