5.2.6. End of Study Visits (D63 \pm 2 days)

All subjects willing to carry on the study treatment will be able to take part in an open-label study (ABX464-102).

In any other cases, the subjects will perform an End of Study Visit (EoS) within a week after last dosing. Subjects will be treated according to the standard of care since the last day of study treatment.

Following examinations/procedures should be performed:

- Physical examination and vital signs;
- Body weight;
- Hematology and Biochemistry;
- Partial Mayo Score;
- 12 leads ECG;
- Faecal calprotectin;
- Adverse Events reporting.

NB#1: In case of premature discontinuation occurring during the treatment phase (D0-D55), the above examinations should be performed as an End of Study Visit.

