5.3.10. Pharmacokinetics

The main objective of the PK analysis is to evaluate potential PK specificities of ABX464 in subjects suffering from active UC.

ABX464 was shown to have a very short $t_{1/2}$ (1 to 2 h), so steady-state is virtually reached at the second administration, while NGlcABX464 has a $t_{1/2}$ of 90 to 110 h, meaning that steady-state is reached after 19 to 22 days of administration.

PK analysis will be performed in the first 9 subjects enrolled in this study at Week 0 and Week 4. A first blood sample (reference) will be collected on the first day of treatment before any drug administration then blood samples will be collected for PK purpose at, 0.5, 1, 1.5, 2, 2.5, 3, 4, 8 and 12 post-dose samples

A total of 10 blood samples per subject will be collected for PK purpose and sent to ATLANBIO for Bioanalyses.

Study code: ABX464-101

Blood samples for determination of ABX464, NGlcABX464, Hydroxyl ABX464 glucuronide and/ will be collected from all subjects using direct venipuncture or an indwelling catheter.

Then, the following PK parameters will be derived for ABX464 and NGlcABX464 for each subject:

- C_{max}, t_{max}: the maximum plasma concentration (C_{max}) and the time taken to reach C_{max} (t_{max}) will be obtained directly from the concentration-time data.
- AUC_{0-τ}: the area under the concentration-time curve from time zero to the time of dosing interval τ (12 h post-dose for ABX464 and NGIcABX464). If no concentration can be measured at this time point, AUC_{0-last} (from time zero to the last quantifiable concentration) will be calculated. Both parameters will be presented independently. For both parameters, a linear trapezoidal method will be used.

Moreover, evaluation of steady-state will be made by visual inspection of the pre-dose concentration measurement collected over the study duration.

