8.4. Time Period, and Frequency of Detecting AEs and SAEs

All AEs and SAEs occurring from the time a subject consents to participate in the study until 4 weeks after he or she has completed or discontinued the investigational product must be recorded in the subject's eCRF.

Importantly, SAEs will have to be reported, either by email or by Fax, to SIMBEC ORION within 24 hours of awareness of an SAE.

SIMBEC ORION

[contact]

[contact]

Legislative guidance requires also reporting any **related** SAEs to be reported after the subject finished the study if the investigator becomes aware of them.

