8.5. Recording AEs and SAEs

Severity of AEs will be assessed according to CTC-AE Classification Version 4.0.

Subjects will be asked to report all AEs as part of the procedures performed at each study visit. The site personnel will document all AEs in the subject's medical record. All AEs subsequently must be recorded in the appropriate eCRF sections.

The following points must be recorded for each event:

- A description of the event in medical terms, not as reported by the subject;
- · Date of onset (start date);
- Date of resolution (stop date);
- The time of onset with respect to administering the investigational product;
- The severity of the sign/symptom or clinically significant abnormal laboratory value according to CTC-AE Classification;
- The causal relationship between the investigational product and the occurrence of each AE. This
 will be assessed by each investigator using clinical judgment. Alternative causes, such as natural
 history of the underlying diseases, concomitant medications, other risk factors and the temporal
 relationship of the event to the investigational product will have to be considered. The causality of
 all AEs should be assessed by the investigator with the following question: Is there a reasonable
 possibility that the AE may have been caused by the investigational product? And answered "NO"
 (if not related) and "YES" (if related);
- Action taken regarding the investigational product:
 - o No action;
 - o Temporary discontinuation;
 - Permanent discontinuation;
 - Subject's outcome:
 - Recovered without sequelae / resolved without sequelae;
 - Recovered with sequelae / resolved with sequelae;
 - o Recovering/Resolving;
 - o On-going;
 - o Fatal (for SAEs only).

If in any one subject, the same AE occurs on several occasions, the AE in question must be documented and assessed anew each time.

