3 STUDY DESIGN

3.1 OVERVIEW

This is a Phase IIa, eight-week, double-blind, placebo-controlled randomised study aimed at evaluating the safety and efficacy of ABX464 given once a day (o.d.) at 50 mg, followed by a one-month follow-up

period, in subjects with moderate to severe active ulcerative colitis (UC), who have failed or are intolerant to immunomodulators, anti-TNF α , vedolizumab and/or corticosteroids.

Eligible subjects will be recruited to up to 20 sites in France, Belgium, Poland, Germany, Austria and Hungary from Q3 2017 – Q2 2018 during the overall study period of Q2 2017 – Q3 2018. A total of 30 subjects will be randomised using a 2:1 ratio, where for every two subjects randomised to receive ABX464, one subject will be randomised to receive placebo. Thus 20 subjects will be randomised to receive ABX464 and 10 subjects will be randomised to receive placebo. Randomisation will be stratified according to concomitant treatment with corticosteroids (yes, no) and previous biologics exposure (yes, no).

The dose of 50 mg of the study drug has been selected based on the reassuring safety data accumulated on the 50 mg o.d. from previous studies and the high exposure in ABX464-NGluc (active metabolite) at this dose. A Data Safety Monitoring Board (DSMB) will meet after every three subjects are recruited in order to review the safety profile of this dose level on a regular basis and to recommend, if appropriate, the continuation of the study.

The total duration of the study will be approximately 11 weeks. Subjects will be enrolled at a screening visit, two weeks prior to the first dosing, and eligible subjects will be treated for a total of eight weeks. All subjects willing to continue with the study treatment will be able to take part in a follow-up open-label study, ABX464-102. Subjects who do not enter the open-label study will exit the study and need to perform their end of study (EoS) visit within a week after the last dosing. These subjects will be treated according to the standard of care.

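### The plan states a one-month follow-up and a 4-week adverse event window, but schedules no contact later than about one week after the last dose

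*Protocol*

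**What the plan says.** **Longer follow-up.** Protocol 3.1.1 describes eight weeks of double-blind treatment "followed by a one-month follow-up period", and SAP 3.1 says the same ("followed by a one-month follow-up"). Protocol 8.4 requires that all AEs and SAEs from consent "until 4 weeks after he or she has completed or discontinued the investigational product must be recorded". The note in Protocol 8.1 sets a 4-week period after the treatment visits and allows an extension if there is strong suspicion that drug has not been eliminated. Protocol 8.3.2 applies 4 weeks after the last dose to pregnancy information.

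**Shorter schedule.** Protocol 3.2 has subjects who do not continue into ABX464-102 leave after an end-of-study (EoS) visit: "Thus, the total duration of the study participation is 11 weeks". Protocol 5.2.6 states that "the subjects will perform an End of Study Visit (EoS) within a week after last dosing". The flow charts (Protocol 5.1, SAP 16.1) and SAP 3.4 put that visit at Day 63 ±2 and show nothing after it. SAP 3.1, which carries the one-month follow-up, also says: "The total duration of the study will be approximately 11 weeks".

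**How events are found.** Protocol 8.5: "Subjects will be asked to report all AEs as part of the procedures performed at each study visit". No telephone contact is described.

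**How they are counted.** SAP 11.4.1 runs the treatment-emergent (TEAE) window from first dose to study closure or withdrawal. Period 2 is everything after Day 56, with no end given there or in Protocol 9.3.

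**Pharmacology.** Protocol 3.1.1 calls the glucuronide the active metabolite. Protocol 5.3.10 gives it a half-life of 90 to 110 h, "meaning that steady-state is reached after 19 to 22 days of administration".

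**The concern.** The primary objective is safety and the primary endpoint is TEAEs on ABX464 against placebo. The documents create a duty to record events for 4 weeks after treatment, but give sites no procedure for meeting it in the last three of those weeks. A site that follows the flow chart completes a non-continuing subject at about Day 63. An event after that reaches the database only if the subject volunteers it or the site happens to learn of it. The same holds for pregnancies, for which the last scheduled test is at Day 56 (Protocol 5.3.2).

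Those weeks are not pharmacologically empty. A metabolite that takes about three weeks to reach steady state takes about as long to wash out, so scheduled observation ends while a material fraction is still present.

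The gap reaches the analysis in two places. SAP 11.4.1 and the table list in SAP 14.1 plan a full set of Period 2 tables, where a low count could reflect few contacts as well as few events. The primary test compares all TEAEs, and its window is not cut at Day 56, so post-treatment events enter it from a period with no fixed end and mostly passive ascertainment.

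**Working it through.** **1. Reproduce the stated duration.** Inputs: screening 2 weeks before first dose and treatment for 8 weeks (Protocol 3.2); EoS within 1 week of last dosing (Protocol 3.2, 5.2.6).

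2 + 8 + 1 = 11 weeks, which matches the plan exactly. The 11 weeks therefore contain one week off drug. Taking the stated month as 4 weeks, 2 + 8 + 4 = 14 weeks, with the last contact near Day 56 + 28 = Day 84.

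**2. Share of the recording window with scheduled contact.**

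- Completer, last dose Day 56, EoS Day 63: 7 of 28 days = 25%, leaving 28 − 7 = 21 days.
- Across the ±2-day window (Day 61 to Day 65): 5/28 = 18% to 9/28 = 32%.
- Early discontinuer: Protocol 5.2.6 says the examinations are done as an EoS visit but does not fix the day. If it falls 0 to 7 days after the last dose, 28 to 21 days remain.

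**3. Check the half-life against the stated time to steady state.** Five half-lives: 5 × 90 / 24 = 18.8 days and 5 × 110 / 24 = 22.9 days. This agrees with the protocol's 19 to 22 days, so its figures are mutually consistent.

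**4. Metabolite remaining.** Assuming first-order elimination, fraction = 2^(−24 × days / half-life).

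| Days after last dose | Half-life 90 h | Half-life 110 h |
|---|---|---|
| 5 (Day 61) | 39.7% | 46.9% |
| 7 (Day 63) | 27.4% | 34.7% |
| 8 (Day 63, if last dose was Day 55) | 22.8% | 29.8% |
| 9 (Day 65) | 19% | 25.6% |
| 28 (Day 84) | 0.6% | 1.4% |

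For the 7-day row: 2^(−168/90) = 0.274 and 2^(−168/110) = 0.347. Five half-lives after a Day 56 dose end at about Day 75 to Day 79, inside the 4-week window but after the last visit.

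**5. Who is affected.** Subjects entering ABX464-102 continue study treatment and have no off-drug period here. The rest, including early discontinuers, are affected. The documents do not give their number; among the 30 planned subjects it could lie anywhere from 0 to 30. Protocol 5.2.6 reserves the EoS visit for those who do not roll over, whereas Protocol 7.3 asks it of every subject.

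**The case against.** A reader might infer that off-drug safety is not observed at all. The documents do not support that. The EoS visit collects adverse events, laboratory tests, ECG, vital signs and a physical examination (Protocol 5.2.6). Protocol 8.4 still obliges sites to record events to 4 weeks, and to report related SAEs they learn of after the subject has finished. Protocol 5.3.7 has clinically significant laboratory abnormalities followed to resolution. What is missing is a scheduled contact in weeks 2 to 4.

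A reader might also infer that early discontinuers get almost no off-drug observation. That assumes an EoS visit on the stopping day, which the text does not fix.

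The half-life argument has another side. If 27–35% of the metabolite remains at Day 63, then under the same model 65–73% of the post-dose exposure has already occurred, so the observed week holds most of it. The legible text names no delayed or withdrawal toxicity. However, the background sections are not readable in this copy, so a rationale for one week may exist. The extension clause in Protocol 8.1 shows that slow elimination was considered, although it adds no visit.

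Finally, a reader might conclude that the primary comparison is compromised, or that an empty Period 2 table would mislead. Day 0–56 is untouched, both blinded arms share one schedule, and how many events would be missed, and in which direction, cannot be derived from the documents.

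These points limit the consequence. They do not reconcile a one-month follow-up with an 11-week schedule, and a recording duty is weaker than a scheduled question when events are elicited at visits.

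**Conclusion.** The concern holds as a contradiction with a limited effect on the data. For subjects who do not enter ABX464-102, safety beyond about one week off drug is not actively observed: about 21 of the 28 days have passive capture only, or 21 to 28 for early discontinuers. On the protocol's own half-life, 27–35% of the active metabolite remains 7 days after the last dose, against about 1% at the end of the stated window.

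The Period 2 tables and the post-Day-56 part of the all-TEAE primary comparison are affected. The off-drug data also come from a self-selected subset, those who stop early or choose not to continue.

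This rests on first-order elimination, a last dose at Day 55 or 56, one month read as 4 weeks, and no contact arrangement in documents outside the protocol and SAP. It should be corrected, but it does not undermine the trial.

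**What to change.** Reconcile Protocol 3.1.1 and SAP 3.1 with Protocol 3.2, 5.1, 5.2.6, 7.3 and 8.4 and with SAP 3.4. To deliver the stated follow-up:

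- Add to the flow chart and to Protocol 5.2.6 and 7.3 one telephone contact on adverse events and pregnancy, about 4 weeks after the last ABX464-101 dose, for every subject who does not roll over, including early discontinuers.
- State when the EoS visit falls after early discontinuation, and whether subjects entering ABX464-102 have one.
- Restate participation as up to about 14 weeks for subjects who do not roll over.
- In SAP 11.4.1 and Protocol 9.3, give the TEAE window and Period 2 the same 4-week end. Without this, an event found at the added contact might not count, above all in a withdrawn subject, whose window now closes at withdrawal.

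The cost is a short amendment, one call per exiting subject (at most about 30, plus any replaced subjects) and a last-subject-out date up to about 3 weeks later. No dose, treatment or stopping rule changes.

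If the sponsor prefers to keep the schedule, remove the one-month follow-up statement from both documents, align the recording window with what is scheduled, and state that active off-drug follow-up lasts about one week.
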